#### 1.5.3 Part 1/Part 2 safety analysis

As of 26 October 2018, enrollment in study ARQ 087-101 had been completed, with a total of 119 patients enrolled and evaluated for the safety and tolerability of derazantinib. 61 patients were enrolled in Dose Escalation / Food Effect cohorts: three were dosed at 25 mg QOD, six at 25 mg QD, six at 50 mg QD, four at 100 mg QD, five at 150 mg QD, five at 200 mg QD, seven at 250 mg QD, six at 325 mg QD, seven at 425 mg QD, five at 400 mg QD, and an additional seven patients were dosed at 400 mg QD under fed conditions. The RP2D was defined as 300 mg QD.

Due to dose-dependent increases in the overall number of drug-related AEs and no significant difference in derazantinib PK exposure compared to higher dose levels (up to 425 mg QD), the dose of 300 mg QD was defined as the RP2D. There were three events of CTCAE Grade 3 AST increased that were defined to be a DLT. All these events resolved

after dose reduction (one patient) or treatment discontinuation (two patients). The first event was observed at a dose level of 250 mg QD (dose was reduced to 200 mg QD) and the two other events were observed at 425 mg QD. No DLTs were reported in the 12 patients treated at the dose level of 400 mg QD with or without food. However, there was an increase in the number of drug-related AEs at high dose levels (400-425 mg QD) compared to medium dose levels (250-325 mg QD), thus the dose of 300 mg QD was defined as RP2D. Additionally, at near steady state conditions (Day 22), derazantinib concentrations are dose proportional in the dose range of 100 to 300 mg QD dosing which supports a manageable and predictable dose reduction plan from 300 to 200 mg OD and from 200 to 100 mg QD.

A total of 58 patients were enrolled and treated at the RP2D level. The enrollment of patients with advanced solid tumors with FGFR GAs was completed in January 2017. All patients had discontinued treatment as of 26 October 2018. The most common reasons for discontinuing treatment were radiological disease progression (per RECIST) 69/119 (58.0%) and clinical disease progression 24/119 (20.2%).

At least one drug-related AE was reported in 102 of 119 patients (85.7%), with most being mild or moderate in severity. The five most common derazantinib-related AEs were nausea (42.9%), fatigue (41.2%), AST increased (26.1%), vomiting (21.8%), and diarrhea (21.0%). Derazantinib-related severe (≥ CTCAE grade 3) AEs were reported in 23/119 patients (19.3%).

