# 2.2 MODIFIED INTENT-TO-TREAT (MITT) POPULATION

The mITT population will include all patients in the Safety/ITT population, who have at least one postbaseline disease assessment (at least one post-baseline imaging assessment in accordance with RECIST 1.1, or documented clinical progression [every effort should be made to objectively assess radiographic progression]), or reported death during the treatment period

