PFS will be calculated as the time from first dose of study drug until disease progression as assessed by BICR, or death from any cause, whichever occurs first. Patients who either have no baseline tumor evaluation or have no post-baseline tumor evaluation will be censored at date of first dose. Patients who discontinue treatment due to reasons other than disease progression by BICR or death will be censored in the PFS analyses as the date of their last tumor evaluation prior to EOT. Patients who progress or die after missing  $\geq 2$  consecutive scheduled tumor assessments will be censored at the date of the last tumor evaluation prior to progression or death. Any disease progression as assessed by BICR, or death occurring after end of treatment visit are not taken into account as a PFS event. For missing end of treatment visit date, a +7 day window compared to the maximum of last dose date, last on treatment visit date will be applied to create a tentative end of treatment visit date and a cut-off for death occurring after this date.

The rules for censoring PFS are summarized in the table below:

Situation	Date of progression or consoring	Outcome
No baseline tumor assessments	Date of first dose	Censored
No post-baseline tumor evaluation	Date of first dose	Censored
Documented radiological	Date of radiological assessment of measured	Progressed
progression	lesions up to EOT	
No radiological progression	Date of last radiological assessment of measured	Censored
	lesions up to EOT	
Treatment discontinuation for	Date of last radiological assessment of measured	Censored
reasons other than radiological	lesions up to EOT	
disease progression by BICR or		
death		
Death before first PD assessment	Date of death	Progressed
Death between adequate assessment	Date of death	Progressed
visits		
Death or radiological progression	Date of last radiological assessment of measured	Censored
after more than two missed tumor	lesions prior to progression or death	
assessment or after end of treatment		

Table 2: Censoring scheme for PFS

The hypothesis being tested is:

Null Hypothesis H0: PFS  $3 \le 0.45$  and Alternative Hypothesis HA: PFS 3 > 0.45

Where PFS 3 is the proportion of patients with a PFS > 3 months (i.e. > 91 days).

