A Simon's two-stage design will be used, with approximately 15 patients in Stage 1, and an additional 28 patients if the study proceeds to Stage 2.  $H_0$  will be rejected if a PFS 3 is observed in 25 or more of these 43 patients. The type I error rate is 0.0481, and power is approximately 0.8 when the true PFS 3 rate for derazantinib is p1 = 0.65.

Point estimates, exact 2-sided 95% confidence intervals (Clopper-Pearson) and associated p-value will be provided.

PFS will be analyzed using Kaplan-Meier methodology (Kaplan & Meier 1958). The median duration of PFS will be presented along with the standard error and 2-sided 95% CI. If they are calculable, the 25th and 75th percentiles and the 2-sided 95% CIs around the percentiles will be presented. Kaplan-Meier estimates at 3, 6, 9 and 12 months will also be presented. The Kaplan-Meier survival curves will also be presented.

Additional PFS sensitivity analyses which consider alternative censoring methods as outlined in FDA guidelines (FDA 2018, FDA 2015) will be conducted in the same manner, as described above. These will be performed for the Safety/ITT and mITT populations:

- Sensitivity analysis 1 in Table 3 uses a conservative approach by assigning the date of discontinuation, or missed tumor assessment followed by PD or death as an event date.
- Sensitivity analysis 2 in Table 4 includes clinical progression as an event.
- Sensitivity analysis 3 in Table 5 evaluates PFS including post EOT radiological assessments.

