# Table 3: Censoring scheme for PFS - sensitivity analysis 1 (any change considered as progression event)

Situation	Date of progression or censoring	Outcome
No baseline tumor assessments	Date of first dose	Censored
No post-baseline tumor evaluation	Date of first dose	Censored
Documented radiological progression	Date of radiological assessment of	Progressed
between scheduled visits	measured lesions	
No radiological progression	Date of last radiological assessment	Censored
	of measured lesions	
Treatment discontinuation for reasons	Date of discontinuation	Progressed
other than radiological disease progression		
by BICR or death		
Death before first PD assessment	Date of death	Progressed
Death between adequate assessment visits	Date of death	Progressed
Death or radiological progression after	Date of first missed tumor	Progressed
more than two missed tumor assessment	assessment	

Table 4. 4	Concoring	achama far	DEC	concitivity	analyzia 7	(included	alimiaal	nnognogion)
1 abie 4: v	Censoring	scheme for		- sensitivity		uncidaes	Списа	progression
			~			(		

Situation	Date of progression or censoring	Outcome
No baseline tumor assessments	Date of first dose	Censored
No post-baseline tumor evaluation	Date of first dose	Censored
Documented radiological progression	Date of radiological assessment of	Progressed
	measured lesions up to EOT	
No radiological progression, no clinical	Date of radiological assessment of	Censored
progression	measured lesions up to EOT	
Clinical progression	Date of clinical progression	Progressed
Treatment discontinuation for reasons	Date of radiological assessment of	Censored
other than radiological disease progression	measured lesions up to EOT	
by BICR, clinical progression or death		
Death before first PD assessment	Date of death	Progressed
Death between adequate assessment visits	Date of death	Progressed
Death or radiological progression or	Date of last radiological assessment	Censored
clinical progression after more than two	of measured lesions prior to	
missed tumor assessment or after end of	progression or clinical progression	
treatment	or death	

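### In SAP Tables 3 and 4 the row that censors patients without a post-baseline scan at first dose conflicts with the event rows that define PFS sensitivity analyses 1 and 2, and no precedence is stated

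*SAP*

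**What the plan says.** SAP 3.2.7.1 (Substudy 2) sets out the main PFS rule and then three sensitivity analyses.

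- **Main rule.** "Patients who either have no baseline tumor evaluation or have no post-baseline tumor evaluation will be censored at date of first dose". No exception is given.
- **Aim of analysis 1.** "Sensitivity analysis 1 in Table 3 uses a conservative approach by assigning the date of discontinuation", with an event also assigned for missed assessments followed by progression or death.
- **Aim of analysis 2.** "Sensitivity analysis 2 in Table 4 includes clinical progression as an event".
- **How they are run.** The sensitivity analyses "will be conducted in the same manner, as described above", in the Safety/ITT and mITT populations.
- **Tables 3 and 4.** Both contain the row "No post-baseline tumor evaluation", with date of first dose and outcome censored. Table 3 also makes treatment discontinuation for reasons other than central radiological progression or death an event on its date. Table 4 also makes clinical progression an event on its date. Both make death before the first progression assessment an event.
- **Who is in the analysis.** Safety/ITT (SAP 2.1) requires no scan. SAP 2.2 admits a patient to mITT on a post-baseline image "or documented clinical progression [every effort should be made to objectively assess radiographic progression]", or on death during treatment.

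SAP 3.2.7.2.1 applies the same PFS analysis to Substudy 1.

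**The concern.** The two analyses exist to show what happens to PFS when early stops or clinical progression are no longer treated as uninformative censoring. The patients who test this most sharply are those who deteriorate or stop before the first scheduled scan at Cycle 3 Day 1 (Day 57). The tables give these patients two contradictory outcomes. If the no-scan row is applied, the patients whom the analysis was built to count are censored at time zero, and the result drifts back towards the main analysis. Agreement between the two would then say little about robustness. The error can go only one way, towards longer PFS.

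**Working it through.** **The rows, for a living patient with no post-baseline scan**

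| Patient | Table 3 | Table 4 |
|---|---|---|
| Stops for documented clinical progression | no-scan row: censored at first dose; discontinuation row: event | no-scan row: censored at first dose; clinical-progression row: event |
| Stops for toxicity or another reason | no-scan row: censored at first dose; discontinuation row: event | censored by design, so no conflict |

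In mITT only the first line arises, because a toxicity stop without a scan does not meet SAP 2.2. In Safety/ITT both lines arise.

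**Which row the text favours.** The main-analysis rule is unconditional. Table 4 also rewords two other generic censoring rows (no radiological progression; discontinuation for other reasons) so that they exclude clinical progression, but leaves the no-scan row unchanged. A programmer could reasonably censor. Against that, the stated aims favour the event rows. The SAP does not settle it.

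**Plan figures nearby.** The plan gives no figure for this point. The only design figures in the section are for the Simon design (continue with at least 8 of 15, reject with at least 25 of 43). The exact two-stage binomial gives a type I error of 0.0481 at 0.45 and power of 0.8035 at 0.65, matching the stated 0.0481 and about 0.8. They do not depend on Tables 3 and 4.

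**Size if the no-scan row wins.** Let k of n patients be affected. Censored at first dose, they leave before any event, so the curve is that of the other n − k patients. If they are counted as events before 3 months, and there is no other censoring by then,

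S_event(3) = S_censored(3) × (n − k)/n.

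Inputs:
- median PFS 5.7 months for fusion patients (Protocol 1.5.5);
- exponential times in the unaffected patients (assumption);
- affected share f = k/n of 3% to 10% (assumption; the documents give no count).

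S_censored(3) = 2^(−3/5.7) = 0.694. With the affected patients counted as events, the median solves (1 − f) × 2^(−t/5.7) = 0.5, so t = 5.7 × [1 + log2(1 − f)].

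| f | 3-month estimate, censored | 3-month estimate, event | Median, censored | Median, event |
|---|---|---|---|---|
| 3% | 0.694 | 0.694 × 0.97 = 0.673 | 5.7 | 5.45 |
| 5% | 0.694 | 0.694 × 0.95 = 0.660 | 5.7 | 5.28 |
| 8% | 0.694 | 0.694 × 0.92 = 0.639 | 5.7 | 5.01 |
| 10% | 0.694 | 0.694 × 0.90 = 0.625 | 5.7 | 4.83 |

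**Check with an explicit Kaplan-Meier estimator** (affected patients either censored at day 1 or events at about day 28, read at day 91):

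- n = 100, median 5.7 months: 0.698 to 0.670 for k = 4; 0.696 to 0.640 for k = 8; 0.700 to 0.630 for k = 10.
- n = 43, median 6.7 months (mutation/amplification patients, Protocol 1.5.6): 0.732 to 0.698 for k = 2; 0.744 to 0.674 for k = 4.

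These agree with the formula up to the steps of a finite sample.

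**The case against.** **The tables work only if specific event rows override generic censoring rows.** In Table 3 the row for no radiological progression (censored) stands above the discontinuation row (event). If the first matching row won, the discontinuation row would never apply to anyone without radiological progression, and analysis 1 would be empty. This stands. Row order is not the rule, so one may not infer that the no-scan row prevails because it is listed earlier. It does not remove the conflict, because the override is nowhere stated and the no-scan rule is written as absolute in the main text.

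**The main rule need not carry over.** These are introduced as alternative censoring methods, and the sentence on running them in the same manner follows the Kaplan-Meier paragraph, so it may refer only to estimation. That is a fair reading. It leaves the outcome open rather than resolved.

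**The group should be small.** Protocol 5.4.4 and 6.9 call for an End of Treatment scan when the last one was more than 28 days earlier or did not show progression, and SAP 2.2 asks for every effort to assess progression objectively. This stands and limits the size. It does not bring the number to zero: Protocol 6.9 also says that a discontinuation scan is not mandatory if one exists within the previous 28 days, and for a very early stop that could be the baseline scan.

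**No decision rests on these analyses.** This is correct. They are descriptive, and the SAP gives them no confirmatory role.

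**Conclusion.** The contradiction is real, and it lies in how the rows overlap. The SAP does not establish that these patients are censored. If they are, PFS in sensitivity analyses 1 and 2 is too long. Under the stated assumptions (3% to 10% affected, exponential times, median 5.7 months, no other censoring before 3 months), the 3-month estimate is about 0.69 where it should be about 0.67 to 0.62, an excess of roughly 2 to 7 points. The true size is unknown.

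Four stronger readings are tempting and not supported:

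- **That all early dropouts are lost.** Toxicity stops conflict only in Table 3, and deaths have their own event row and are outside this point.
- **That the Substudy 2 primary test is biased.** PFS3 is a binary count of PFS beyond 91 days. A patient censored at first dose is not a success, and the test does not use Tables 3 and 4. For ORR, SAP 3.2.7.1 counts patients without assessments as non-responders.
- **That about 20% are affected.** The 24 of 119 patients (20.2%) who stopped for clinical progression in the phase 1/2 study (Protocol 1.5.3) cover all doses, tumor types and times on treatment, so this figure does not give the share before a first scan.
- **That the excess can be set against the planned rise from 0.45 to 0.65.** That contrast belongs to the binary endpoint in Substudy 2, while the 5.7-month median comes from fusion patients.

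The point merits a correction before the analysis is run, because the direction of any error is known and the remedy is a line in each table.

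**What to change.** In Table 3, limit the row to patients with no post-baseline tumor evaluation and no treatment discontinuation event or death. In Table 4, limit it to patients with no post-baseline tumor evaluation and no clinical progression or death. Alternatively, state once that in both tables the event rows take precedence over the no-scan row. In either case, report for each substudy and analysis population how many patients are censored at first dose, so that a reader can judge the remaining effect.

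The cost is one line in each of two tables and one count in the output. No new data are needed. The only downside is that the sensitivity estimates of PFS may be slightly less favourable.

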# Table 3: Censoring scheme for PFS - sensitivity analysis 1 (any change considered as progression event)

Situation	Date of progression or censoring	Outcome
No baseline tumor assessments	Date of first dose	Censored
No post-baseline tumor evaluation	Date of first dose	Censored
Documented radiological progression	Date of radiological assessment of	Progressed
between scheduled visits	measured lesions	
No radiological progression	Date of last radiological assessment	Censored
	of measured lesions	
Treatment discontinuation for reasons	Date of discontinuation	Progressed
other than radiological disease progression		
by BICR or death		
Death before first PD assessment	Date of death	Progressed
Death between adequate assessment visits	Date of death	Progressed
Death or radiological progression after	Date of first missed tumor	Progressed
more than two missed tumor assessment	assessment	

Table 4. 4	Concoring	achama far	DEC	concitivity	analyzia 7	(included	alimiaal	nnognogion)
1 abie 4: v	Censoring	scheme for		- sensitivity		uncidaes	Списа	progression
			~			(		

Situation	Date of progression or censoring	Outcome
No baseline tumor assessments	Date of first dose	Censored
No post-baseline tumor evaluation	Date of first dose	Censored
Documented radiological progression	Date of radiological assessment of	Progressed
	measured lesions up to EOT	
No radiological progression, no clinical	Date of radiological assessment of	Censored
progression	measured lesions up to EOT	
Clinical progression	Date of clinical progression	Progressed
Treatment discontinuation for reasons	Date of radiological assessment of	Censored
other than radiological disease progression	measured lesions up to EOT	
by BICR, clinical progression or death		
Death before first PD assessment	Date of death	Progressed
Death between adequate assessment visits	Date of death	Progressed
Death or radiological progression or	Date of last radiological assessment	Censored
clinical progression after more than two	of measured lesions prior to	
missed tumor assessment or after end of	progression or clinical progression	
treatment	or death	

# Table 5: Censoring scheme for PFS - sensitivity analysis 3 (including post EOT assessments)

Situation	Date of progression or censoring	Outcome
No baseline tumor assessments	Date of first dose	Censored
No post-baseline tumor evaluation	Date of first dose	Censored
Documented radiological progression	Date of radiological assessment of	Progressed
	measured lesions	
No progression, or new anticancer	Earliest date of:	Censored
treatment started	- last radiological	
	assessment of measured	
	lesions, including post	
	EOT	
	- new anticancer	
	treatment	
Death before first PD assessment	Date of death	Progressed
Death between adequate assessment visits	Date of death	Progressed
Death or progression after more than two	Date of last radiological assessment	Censored
missed tumor assessment	of measured lesions prior to	
	progression or death	

## 3.2.7.2 Analyses of Secondary Efficacy Variables

### 3.2.7.2.1 PFS (Substudy 1 and Substudy 2)

PFS as assessed by BICR will be analyzed as detailed in Section 3.2.7.1 for primary efficacy analysis for Substudy 2.

# 3.2.7.2.2 DoR (Substudy 1 and Substudy 2)

DoR (months) will be calculated from the first date of documented objective tumor response (confirmed CR or PR) to disease progression as assessed by BICR or death. If a patient is discontinued or is lost to followup with no documentation of progressive disease, DoR is defined as the time from the date of the first documentation of OR to the date of the last tumor assessment as a censored value.

DoR will be derived only for patients who have the best overall response of CR or PR.

DoR will be analyzed using Kaplan-Meier methodology (Kaplan & Meier 1958). The median DoR will be presented along with the standard error and 2-sided 95% CI. If they are calculable, the 25th and 75th percentiles and the 2-sided 95% CIs around the percentiles will be presented. Kaplan-Meier estimates at 3, 6, 9 and 12 months will also be presented. The Kaplan-Meier survival curves will also be presented.

The date of first study drug dose, documented objective tumor response, disease progression, death, last tumor assessment, last contact and DoR days will be reported in a by-patient listing.

#### 3.2.7.2.3 OS (Substudy 1 and Substudy 2)

OS time (months) will be calculated from the first date of receiving study drug until death from any cause. Any patient without a date of death in the database at the time the survival analyses are performed will be censored at the time of their last study contact. OS will be performed for the Safety/ITT population.

OS will be analyzed using Kaplan-Meier methodology (Kaplan & Meier 1958). The median duration of OS will be presented along with the standard error and 2-sided 95% CI. If they are calculable, the 25th and 75th percentiles and the 2-sided 95% CIs around the percentiles will be presented. Kaplan-Meier estimates at 3, 6, 9 and 12 months will also be presented. The Kaplan-Meier survival curves will also be presented.

The date of first study drug dose, death, last study contact and OS days will be reported in a by-patient listing.

#### 3.2.7.2.4 ORR (Substudy 2)

ORR will be considered a secondary efficacy endpoint in Substudy 2 and analyzed in the same way as stated in Section 3.2.7.1.

#### 3.2.7.2.5 PRO Assessments (Substudy 1 and Substudy 2)

For each assessment the minimally important difference (MID) in a score at C3D1 and C5D1 will be determined following the recent protocol by the EORTC Quality of Life Group (Musoro 2018). Patients with complete data will be categorized into five mutually exclusive clinical change groups (CCG) reflecting the five possible levels of change. For each pair of timepoints (Change in summary score from baseline at

C3D1 and Change in summary score from C3D1 at C5D1), a patient can thus belong to only one CCG category. Two methods for determining the MID will be explored:

#### 1. Mean Change Method

For a given mean absolute change in PRO assessment scale summary score: the MID for improvement is equal to the mean summary score of the 'small positive change' CCG (somewhat better now than 6 weeks ago) and the MID for deterioration is equal to the mean summary score of the 'small negative change' CCG (somewhat worse now than 6 weeks ago). The mean summary score of the 'small change' CCGs and that of the 'no change' CCG will be compared and reported. If the mean summary score for 'no change' CCG is similar to any of the two 'small change' CCGs, the estimated MID may be considered doubtful. No a priori rule will be established to determine if mean summary scores are sufficiently similar to determine MID to be doubtful.

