#### 2. Linear Regression

For a given absolute change in PRO assessment scale summary score: the estimate of the numerical change in summary score that is associated with the transition between adjacent CCG categories will be determined using linear regression. Separate models will be fitted for improving and deteriorating scores based on the anchor. The outcome variable is the PRO assessment summary score, and the covariate is a binary anchor variable; coded as 'no change'=0 and 'small positive change'=1 for model on improvement (Other CCG categories are excluded from the linear regression model), and 'no change'=0 and 'small negative change'=1 for model on deterioration (Other CCG categories are excluded from the linear regression model). The resulting  $\beta$ 's (i.e. slope parameters) correspond to the MIDs for improvement and deterioration respectively. No other covariates will be included in these models.

PRO analysis will be performed for the Safety/ITT population.

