#### 3.2.7.2.5.1 G-SET/HTI

G-SET/HTI is a single item, and will be used as an external anchor to determine the minimal important difference of EQ-5D-VAS, EORTC QLQ-C30, and QLQ-BIL21 scales. The G-SET/HTI is a patient-rated change in health between two time periods using a five-point ordinal scale (1=much better now than 8 weeks ago; 2=somewhat better now than 8 weeks ago; 3=about the same as 8 weeks ago; 4=somewhat worse now than 8 weeks ago). G-SET/HTI will be summarized at Cycle 3, Day 1, and Cycle 5, Day 1 by categorical and continuous descriptive statistics.

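### SAP 3.2.7.2.5 contradicts itself on whether the minimally important difference is built from the change in score or from the score itself

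*SAP*

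**What the plan says.** **Where the SAP aims at change.** The introduction to SAP 3.2.7.2.5 defines two intervals, baseline to C3D1 and C3D1 to C5D1, and describes both as changes. The sentence ends: "C3D1 and Change in summary score from C3D1 at C5D1), a patient can thus belong to only one CCG category". The first method is headed Mean Change Method. The Linear Regression text states its target as "the estimate of the numerical change in summary score that is associated with the transition between adjacent CCG categories". The sections on the QLQ-C30, the QLQ-BIL21 and the EQ-5D VAS then call on both methods to find a minimally important change over the same two intervals.

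**Where the SAP names the score.** In the Mean Change Method one sentence holds both ideas. It opens by naming the mean change, and then says that "the MID for improvement is equal to the mean summary score of the" group whose patients report being somewhat better. Deterioration is defined in the same way. The built-in check is also worded as a comparison of scores: "If the mean summary score for 'no change' CCG is similar to any of the two 'small change' CCGs", the MID may be considered doubtful. In the regression, "The outcome variable is the PRO assessment summary score, and the covariate is a binary anchor variable", the slopes are taken to be the MIDs, and the text rules out any further covariate.

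**The anchor.** SAP 3.2.7.2.5.1 and Protocol 6.10 give the G-SET/HTI item an 8-week recall, as in "somewhat better now than 8 weeks ago". The Mean Change Method labels the same category "somewhat better now than 6 weeks ago".

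**The concern.** A programmer works from the sentence that defines the quantity, and in both methods that sentence names the score. The shift is not a single dropped word. It occurs in the MID definitions, in the check against the no-change group, and in the regression outcome. The SAP has a separate term for the change in score and does not use it at these places.

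The two methods carry different risks. In the mean change method a literal result would be a typical scale score, and a reviewer of the output would question it. In the regression a literal result is a difference between two group means. It can be of a believable size, so it could pass unnoticed. Excluding other covariates also excludes adjustment for the starting score.

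At stake is the MID that both documents list within a secondary objective (Protocol 2.2, SAP 1.2.2).

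**Working it through.** The documents state no MID value and no sample size or power for this analysis, so there is no figure of the plan's own to reproduce. The check is algebraic, followed by an illustration with assumed inputs.

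**Notation.** For one interval, let B1 and B0 be the mean scores at its start in the small positive change group and the no-change group. Let c1 and c0 be their mean changes. Scores at the end of the interval then average B1 + c1 and B0 + c0. I take the literal wording to mean the score at the end of the interval, because the section refers to the MID in a score at C3D1 and C5D1.

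**Method 1, mean change.**
- On the change in score: MID = c1.
- On the score, read literally: MID = B1 + c1.

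**Method 2, regression.** With a single 0/1 covariate, the least-squares slope is the difference in group means.
- On the change in score: slope = c1 - c0.
- On the score, read literally: slope = (B1 + c1) - (B0 + c0) = (c1 - c0) + (B1 - B0).

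The literal slope is therefore the wanted contrast plus the gap between the groups at the start of the interval. It is correct only when B1 = B0. The same identity holds for the deterioration model, and for the C3D1 to C5D1 interval with the C3D1 score as the starting value.

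**Illustration.** All inputs are assumed; none comes from the documents. On a 0-100 scale, take c1 = 6 and c0 = 0, so the true MID is 6 by either method.

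| B0 (no change) | B1 (small positive) | Gap B1 - B0 | Method 1 literal, B1 + 6 | Method 2 literal, 6 + gap | Either method on change |
|---|---|---|---|---|---|
| 70 | 60 | -10 | 66 | -4 | 6 |
| 70 | 65 | -5 | 71 | 1 | 6 |
| 70 | 70 | 0 | 76 | 6 | 6 |
| 65 | 70 | +5 | 76 | 11 | 6 |
| 60 | 70 | +10 | 76 | 16 | 6 |

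A simulation with an assumed baseline SD of 20 and change SD of 12 gave the same values to within 0.1. The SDs do not enter the expected values.

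**Can a zero gap be assumed?** The groups are formed from patients' own ratings after baseline, not by design, so nothing makes their starting scores equal. The documents do not give the size or direction of any gap.

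**The case against.** The strongest reply is that the intent is clear. The sentence defining the MID opens with a clause about change, under a heading that says the same. The regression states a numerical change as its target. The intervals and the scale sections are also framed as change. On that reading, summary score is shorthand for the change just named. This stands as evidence of intent, and it rules out saying that the SAP plans to analyse score levels. It does not settle what to program, least of all for the regression. Its stated target, a numerical change tied to moving between adjacent categories, can also be read as a difference in score between groups.

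A reader might infer three stronger points that the documents do not support:

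- **That the literal regression returns a baseline difference.** It returns the true contrast plus the gap at the start of the interval, and is right when that gap is zero. A wrong sign needs a gap of opposite sign that exceeds the true contrast. The -4 above rests on an assumed 10-point gap.
- **That the word absolute tells analysts to drop the sign.** The scale sections report change and percent change side by side, so absolute is most naturally the contrast to percent. Improvement and deterioration are defined and modelled separately. Nothing instructs analysts to take magnitudes.
- **That the 6-week label alters the result.** The mismatch is real, but patients are grouped by their recorded answer to an item with 8-week recall, so the label changes no number.

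It is also fair to say that the MID is missing from the endpoint lists (Protocol 3.3.2, SAP 1.3.2), that the SAP describes the two methods as explored, and that Protocol 10.6.2 makes the quality-of-life analysis mainly descriptive. That limits the impact but does not remove the ambiguity.

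**Conclusion.** The concern holds as an internal contradiction: the section aims at change in score, while its operative sentences specify the score. Followed word for word, method 1 gives a group mean (66 to 76 in the illustration, against a true 6), which would be noticed. Method 2 gives -4 to 16 for assumed starting gaps of -10 to +10, and 6 at a gap of zero. Those figures rest on the assumed true MID of 6, the assumed gaps, and a literal reading that uses the score at the end of the interval. The identity behind them does not depend on the chosen values.

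It would go too far to conclude that the secondary MID objective will return something other than an MID. That happens only if the operative sentences are programmed without regard to their context. The reach is confined to the MID part of a secondary, descriptive objective. ORR in Substudy 1 and PFS at 3 months in Substudy 2 are unaffected, and no test, stopping rule or sample size depends on the MID.

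**What to change.** In SAP 3.2.7.2.5:

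1. **Mean Change Method.** In both MID definitions, and in the comparison with the no-change group, replace the mean summary score with the *mean change in summary score*.
2. **Linear Regression.** State the outcome as the *change in summary score (baseline to C3D1; C3D1 to C5D1)*. The remaining model text can stay.
3. **Clerical.** In the Mean Change Method, change both 6-week labels to 8 weeks, to agree with SAP 3.2.7.2.5.1 and Protocol 6.10.

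As an option, say that changes keep their sign, which would remove any doubt about the word absolute.

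The cost is a few words in the SAP. No new data are needed, and no other planned analysis changes.
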